### **3.8 Restrictions**

Beginning at the screening visit, all subjects will undergo a diet and lifestyle stabilization period, and will receive counselling regarding the 2007 China Adult Dyslipidemia Management Guidelines TLC diet (see Appendix E). The following restrictions will be applied to subjects in this study:

- Subjects who were blood donors are not to donate blood during the study or for 3 months following their last dose of study treatment.
- Subjects will fast (water is permitted) and refrain from alcohol consumption for 8 hours before visits requiring blood collection.
- Subjects should refrain from cigarette smoking on the morning of each visit.
- Subjects should be advised to maintain their normal physical activities or exercise routines during the trial.

- Subjects should alert the investigator regarding any elective planned surgery or extended travel.

### **3.9 Discontinuation of investigational product**

Subjects may be discontinued from investigational product in the following situations, at the discretion of the investigator(s):

- Subject decision. The subject is at any time free to discontinue treatment, without prejudice to further treatment.
- An AE that in the opinion of the investigator warrants subject withdrawal.
- Severe non-compliance with the study protocol.
- Withdrawal of informed consent.
- CK >10 x ULN accompanied by muscle pain, tenderness, or weakness; see Appendix D for management of increased creatine kinase.
- ALT or AST >3 x ULN; see Appendix C for further instruction on cases of increases in liver biochemistry and evaluation of Hy's Law.
- Deterioration in the subject's condition that in the opinion of the investigator warrants subject withdrawal.
- At investigator's discretion.
- Development of a condition that made the subject high-risk, such as clinical atherosclerotic disease (MI, transient ischemic attack, stroke, angina pectoris, symptomatic CAD, peripheral arterial disease, abdominal aortic aneurysm) or diabetes mellitus.

Subjects will be monitored to ensure that they are within the entry criteria limits for LDL-C throughout the study. Subjects will be discontinued from the treatment in 1 of 2 circumstances based on a subject's inclusion criteria:

1. Subjects with no additional CVD risk factors other than age and hypertension, and subjects without hypertension who have 3 or more other risk factors (including age) will be discontinued from the treatment if their LDL-C levels are  $\geq 160$  mg/dL (4.1 mmol/L) on 2 consecutive visits during the study.
2. Subjects without hypertension who have fewer than 3 other risk factors (including age) will be discontinued from the treatment if their LDL-C levels are  $\geq 190$  mg/dL (4.9 mmol/L) on 2 consecutive visits during the study.

The results of the LDL-C determinations will remain unblinded to the central laboratory but will be blinded to the investigator and site personnel after screening. A flag on the central laboratory report will notify the investigator that the subject should be removed from the study. The subject will be discontinued from the study and complete the Early Termination visit procedures. Subsequent treatment will be advised by the investigator based on local guidelines.

If the subject is discontinued from investigational product, the principal investigator/sub-investigator will perform the best possible observation(s), test(s) and evaluation(s) as well as give appropriate medication and all possible measures for the safety of the subject. The subject will be required to attend the Early Termination visit (see Section 4.2.11) and to return all study medication.

In cases where a subject has been removed from study treatment for 2 weeks or longer, the AstraZeneca physician or designee needs to be contacted prior to any decision to permanently withdraw or resume investigational product.

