## **12.4 Appendix D Guidance for Management of Muscle Symptoms and Increased Creatine Kinase (CK)**

## **GUIDANCE FOR MANAGEMENT OF MUSCLE SYMPTOMS AND INCREASED CREATINE KINASE (CK)**

- Throughout the study, subjects should be instructed to promptly report unexplained muscle pain or weakness, particularly if associated with malaise or fever. If this occurs, creatine kinase (CK) should be measured as soon as possible.
- If CK is found to be elevated  $\geq 5 \times \text{ULN}$  on routine testing, the subject should be questioned about muscle symptoms.
- A suitably-experienced physician should be involved in deciding appropriate management for the subject. The physician should be alerted to the occurrence of unexplained muscle symptoms, and any CK values  $\geq 5 \times \text{ULN}$  and must take immediate action if CK  $> 10 \times \text{ULN}$ .
- For CK  $> 10 \times \text{ULN}$  with or without muscle symptoms, discontinue study drug.
- For CK 5-10xULN:
  - If symptomatic and no alternative explanation exists, withhold therapy
  - If asymptomatic, or if symptomatic but alternative explanation exists, follow symptoms and CK levels weekly until there is no longer medical concern or symptoms worsen and meet criteria above
- The following questioning and follow-up investigations should be considered:
  - Clarify the nature, duration and intensity of relevant symptoms
  - Clarify and document whether the patient was taking study treatment at the time of the event, or when the last dose of study treatment was taken. Document dosing information in source and report if appropriate (eg, if considered an SAE).
  - Review possible predisposing factors, such as: unaccustomed exercise (including decorating, gardening, etc.), heavy alcohol intake, viral illness (consider performing serology), concomitant medications (e.g. anesthetics, cholesterol -lowering agents – niacin, clofibrate, statins, ezetimibe, glucocorticoids, narcotics, chloroquine, etc.) and consider diagnosis of other conditions which can cause myopathy
    - Physical examination for muscle tenderness, weakness and rash
    - Measure CK again within a few days
    - Measure serum creatinine

- Urinalysis (including myoglobin and sediment)
- Arrange to review the subject again in 4 to 10 days, or earlier if symptoms of myopathy appear or worsen, or if the urine becomes very dark

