- Myopathy is defined as muscle aches or weakness in association with CK increased to  $>10 \times \text{ULN}$ . If myopathy occurs or if on clinical grounds, statin-induced myopathy is diagnosed or suspected, statin therapy should be discontinued. Myopathy should always be recorded as an adverse event, and the AstraZeneca representative must be informed.
- If study treatment is temporarily disrupted, it is suggested that the AstraZeneca representative be consulted before restarting study treatment.
- The AstraZeneca representative should be consulted prior to permanently withdrawing a patient.

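### The CK bullet in Protocol Section 3.9 makes CK >10 x ULN a discretionary stop only with muscle symptoms, while Appendix D, which it cites, stops study drug with or without them.

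*Protocol*

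**What the plan says.** Protocol Section 3.9 opens its list of stopping situations permissively: "Subjects may be discontinued from investigational product in the following situations, at the discretion of the investigator(s". One item in the list is "CK >10 x ULN accompanied by muscle pain, tenderness, or weakness; see Appendix D for management of increased creatine kinase". Another leaves any further stop to the investigator's judgement. After the list come two LDL-C rules written as requirements, which end in removal from the study: "The subject will be discontinued from the study and complete the Early Termination visit procedures". The section then says that, when a subject has been off drug for 2 weeks or more, the sponsor's physician "needs to be contacted prior to any decision to permanently withdraw or resume investigational product".

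Appendix D (Section 12.4) requires a suitably experienced physician to act at once when CK exceeds 10 x ULN. Its next bullet says that at this level, "with or without muscle symptoms, discontinue study drug". Below that, for CK of 5 to 10 x ULN, symptoms do change the action. For follow-up the appendix lists a repeat CK within a few days and "Arrange to review the subject again in 4 to 10 days". For an interrupted treatment, "it is suggested that the AstraZeneca representative be consulted before restarting study treatment".

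In Section 5.2.1, the note under Table 2 refers any CK of 5 x ULN or more to Appendix D without stating a stop. The ALT/AST note beside it does state one.

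**The concern.** Appendix D expressly drops muscle symptoms as a condition above 10 x ULN, and Section 3.9 puts the condition back. Section 3.9 also places CK under optional stops, although the same section has required stops for LDL-C. A reader who goes to 3.9 for the discontinuation criteria meets the narrower and weaker wording first.

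The subject affected is one whose CK exceeds 10 x ULN on a scheduled test and who has no complaint. A site that took the 3.9 bullet as the full criterion, and Appendix D (whose title calls it guidance) as advice on work-up, could keep that subject on drug where Appendix D says to stop. Treatment lasts up to 104 weeks.

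There is a small reporting consequence in the same situation. Under Section 6.3.6, a worsening in a protocol-mandated laboratory value is an adverse event only if it is serious or is the reason for stopping treatment. Whether an asymptomatic CK >10 x ULN enters the adverse event tables could therefore depend on which text the site followed.

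**Working it through.** No arithmetic decides this point. The threshold is the same in both places, so the check is to set the two texts side by side for each kind of subject.

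| CK result | Section 3.9 | Appendix D | Agreement |
|---|---|---|---|
| >10 x ULN, symptoms | CK bullet met; may stop | Stop | Differ in force |
| >10 x ULN, no symptoms | CK bullet not met; only the general discretion item applies | Stop | Differ on symptoms and in force |
| 5 to 10 x ULN, symptoms, no other explanation | No CK item | Withhold | Appendix D alone applies |
| 5 to 10 x ULN, no symptoms or explained | No CK item | Follow weekly | Appendix D alone applies |

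1. **Where symptoms matter.** In Appendix D they change the action only in the 5 to 10 x ULN band. Above 10 x ULN they are ruled out as a condition. The 3.9 bullet is thus narrower than the rule it cites, not a shortened form of it.

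2. **How many texts carry each version.** The stop regardless of symptoms is stated once, in Appendix D. The narrower version is also stated once, in the 3.9 bullet. Appendix D goes on to define myopathy as muscle symptoms with CK >10 x ULN and to call for a stop when myopathy occurs or is suspected clinically. That is a further ground for stopping, not a second symptoms-only version of the CK rule.

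3. **How a site reaches the stricter rule.** There are two pointers in the body text: the 3.9 bullet and the note under Table 2. The second starts at 5 x ULN, so every value above 10 x ULN has already triggered it. A site that follows either pointer arrives at the Appendix D stop, and for that site the mismatch has no effect.

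4. **What remains.** The exposed case is the second row of the table, at a site that follows neither pointer or reads Appendix D as advice only. The documents give no frequency for such CK values and no sign that any site read the text this way.

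5. **What is captured either way.** SAP Section 4.5.2 summarises CK elevations of at least 5 and at least 10 times ULN by treatment group. SAP Section 4.4.7 lists treatment-emergent adverse events in subjects with CK >10 x ULN. The laboratory values are not lost whichever text a site follows.

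**The case against.** The strongest reply is that the two texts can both be obeyed. The 3.9 list is permissive and not exhaustive: it puts withdrawal of consent under investigator discretion and omits the pregnancy stop in Section 6.6.1. Its silence on asymptomatic CK is therefore no instruction to continue drug. Appendix D is called guidance, but its wording at this level is directive, and a site would have to pass over two consecutive bullets to miss it. Both pointers lead there. On this view the 3.9 bullet is a loose summary and the matter is editorial.

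Most of that stands, and it limits the risk. It does not remove the mismatch: the condition that Appendix D excludes is written into the bullet that cites it, and neither pointer states the stop without symptoms.

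Two stronger readings are tempting. A reader might infer that a subject could stay on drug until the next scheduled CK. CK is scheduled at Weeks 13, 39, 65 and 91, so that gap can be 39 − 13 = 26 weeks. The documents do not support such a delay. Appendix D lists an early repeat CK and review, Section 5.2.1 allows extra samples, and the investigator may stop drug at any time. A reader might also count the myopathy rule as a second vote for requiring symptoms; as shown above, it is an additional stop.

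**Conclusion.** The point holds as an internal inconsistency in a patient-safety stopping rule. Section 3.9 and Appendix D disagree on whether symptoms are needed at CK >10 x ULN and on whether the stop is optional. The mismatch can be read directly from the text, and nothing in the readable documents explains it.

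The consequence is limited to a site that treats the 3.9 bullet as the complete criterion and leaves an asymptomatic subject on drug. Its size cannot be quantified from the documents. That any site would do so is an assumption, not a finding. Nothing here bears on the primary CIMT analysis or the sample size. The correction is worth making because the subject matter is safety and the change is very small.

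**What to change.** In Section 3.9, delete the symptom condition from the CK item and move the item out of the discretionary list. State it as its own sentence, apart from the LDL-C rules that remove a subject from the study. For example: *Study drug will be stopped for CK >10 x ULN, with or without muscle symptoms; manage per Appendix D. Consult the sponsor before permanent withdrawal or restart; the Early Termination visit applies only if the stop becomes permanent.*

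The last clause is needed because Sections 3.9 and 3.9.1 send subjects who discontinue product to the Early Termination visit, while Appendix D allows for interruption and restart. The sentence keeps the sponsor-contact steps already in both places. Appendix D and the note under Table 2 can stay as they are.

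The cost is a one-line amendment with ethics committee approval under Section 10.5, or a clarification to the 25 sites that randomized the 543 subjects. It should add no discontinuations beyond those Appendix D already directs, since it sets no new policy on when to stop.

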### **3.9.1 Procedures for discontinuation of a subject from investigational product**

At any time, subjects are free to discontinue investigational product or withdraw from the study (ie, investigational product and assessments – see Section 3.10), without prejudice to further treatment. A subject who decides to discontinue investigational product will always be asked about the reason(s) for discontinuation and the presence of any AEs. If possible, the subject will be seen and assessed by an investigator(s). All AEs will be followed up (see Section 6), and all investigational products should be returned by the subject.

Subjects who discontinue from the investigational product should complete the Early Termination visit procedures.

## **3.10 Criteria for withdrawal**

### **3.10.1 Screen failures**

Screening failures are subjects who do not fulfill the eligibility criteria for the study, and therefore, must not be randomized. These subjects should have the reason for study withdrawal recorded as ‘Incorrect Enrollment’ (ie, subject does not meet the required inclusion/exclusion criteria). This reason for study withdrawal is only valid for screen failures (not randomized subjects).

### **3.10.2 Withdrawal of the informed consent**

Subjects are free to withdraw from the study at any time (investigational product and assessments), without prejudice to further treatment.

A subject who withdraws consent will always be asked about the reason(s) and the presence of any AE. The investigator will follow up AEs outside of the clinical study.

If a subject withdraws from participation in the study, then his/her enrollment/randomization code cannot be reused. Withdrawn subjects will not be replaced.

When a subject is lost to follow-up (ie, fails to return for study visits), a reasonable effort (eg, documented by receipts for certified mailings) will be made to contact the subject to determine why the subject failed to return and to attempt to schedule the Early Termination visit (see Section 4.2.11).

### **3.11 Discontinuation of the study**

The study may be stopped if, in the judgment of AstraZeneca, trial subjects are placed at undue risk because of clinically significant findings that:

- meet individual stopping criteria or are otherwise considered significant
- are assessed as causally related to investigational product
- are not considered to be consistent with continuation of the study

Regardless of the reason for termination, all data available for the subject at the time of discontinuation of follow-up must be recorded in the eCRF. All reasons for discontinuation of treatment must be documented.

In terminating the study, the Sponsor will ensure that adequate consideration is given to the protection of the subjects' interests.

## **4. STUDY PLAN AND TIMING OF PROCEDURES**

A schedule of trial procedures showing the timing of events is presented in [Table 1](#).

**Table 1 Study plan**

Study plan	Screening			Treatment									
	1	2	3	4	5	6	7	8	9	10	11	12	13/ET a
Week number*	-6	-4	-2	0	6	13	26	39	52	65	78	91	104
Informed consent	√												
Randomization				√									
Vital signs	√			√	√	√		√		√		√	√
Height	√												
Body weight	√			√									√
Adverse events	√	√	√	√	√	√	√	√	√	√	√	√	√
Concomitant medications	√			√	√	√	√	√	√	√	√	√	√
Medical history	√												
Physical examination				√									√
ECG				√									√
Chemistry panel	√ b			√	√	√		√ c		√ c		√ c	√
Pregnancy test d	√												
Hematology				√									√
Urine sample e				√									√
Serum lipid profile	√			√	√	√		√		√		√	√
ApoA-I and ApoB				√									√
Risk assessment	√												
IMT		√ f	√ f				√		√		√		√ g
Dispense investigational product				√		√	√	√	√	√	√	√	
Investigational product compliance					√	√	√	√	√	√	√	√	√
TLC counselling h	√			√	√	√	√	√	√	√	√	√	

ALP Alkaline phosphatase; ALT Alanine aminotransferase; Apo Apolipoprotein; AST Aspartate aminotransferase; CK Creatine kinase; ECG Electrocardiogram; ET Early termination; IMT Intima-media thickness; TLC Therapeutic Lifestyle Changes; TSH Thyroid stimulating hormone.

\* Note: The visit window for visits 5-13 is ±7 days.

a In the event of early termination, all non-IMT procedures scheduled for Visit 13 (Week 104) are to be conducted. A single IMT is to be performed on any subject who withdraws after 26 weeks.

b Including TSH at Visit 1.

c Abbreviated chemistry panel including liver function tests (ALT, AST, bilirubin, ALP), serum creatinine, and CK only.

d Urine pregnancy test conducted at study site. Required only for premenopausal females. Those with amenorrhea for at least 1 year are exempt.

e For complete urinalysis.

- f IMT measurements at Visit 2 (Week -4) and Visit 3 (Week -2) must meet inclusion criteria of maximum IMT  $\geq 1.2$  mm and  $< 3.5$  mm.
- g Final IMT procedures will be scheduled before discontinuation of study treatment. The second and final IMT procedure should occur at or before Visit 13 (Week 104), at the time of discontinuation of the study treatment. The 2 IMT procedures for Visit 13 should be performed on different days when possible.
- h TLC counselling is to be reinforced at each clinic visit.

## 4.1 Screening period

Procedures will be performed according to the Study Plan shown in [Table 1](#). At screening, consenting subjects are assessed to ensure that they meet eligibility criteria. Subjects who do not meet these criteria must not be enrolled in the study. All the assessments and procedures for screening period should be performed after informed consent and within 6 weeks prior to subject randomization.

### 4.1.1 Visit 1 (Week -6)

Subjects will be required to fast for 8 hours (water permitted) prior to Visit 1 (Week -6). Those subjects who have failed to fast for 8 hours should return for their blood draw following an 8-hour fasting period. At the visit, the following procedures will be performed:

- Informed consent
- Recording of vital signs
- Measurement of height
- Measurement of body weight
- Recording of AEs
- Review of prior and concomitant medications
- Medical history
- Chemistry panel, including TSH
- Pregnancy test for premenopausal females only. Those with amenorrhea for at least 1 year are exempt.
- Serum lipid profile
- Risk assessment, including calculation of body mass index
- TLC counselling

#### **4.1.2 Visit 2 (Week -4) and Visit 3 (Week -2)**

At Visits 2 and 3, IMT will be performed. Intima-media thickness measurements at both of these visits must meet the inclusion criteria of maximum IMT  $\geq 1.2$  mm and  $< 3.5$  mm, or the subject is not eligible for the study.

IMT measurements at Visit 2 and Visit 3 are not mandatory to be performed on Weeks -4 and -2, respectively, as long as they are performed on different days after Visit 1, and within 6 weeks prior subject randomization. IMT measurement in Visit 3 is to be conducted after Visit 2 IMT measurement result meets inclusion criteria.

AE needs to be recorded in Visit 2 and Visit 3.

## **4.2 Treatment period**

During the Treatment Period, the procedures will be performed according to the Study Plan shown in [Table 1](#). There will be 10 visits during the 104-week treatment period (Visits 4, 5, 6, 7, 8, 9, 10, 11, 12, and 13 at Weeks 0, 6, 13, 26, 39, 52, 65, 78, 91, and 104, respectively). Visits 5-13 will have a visit window of  $\pm 7$  days.

#### **4.2.1 Visit 4 (Week 0; Baseline)**

Visit 4 at Week 0 is the Baseline visit. Subjects will be required to fast for 8 hours (water permitted) prior to Visit 4 (Week 0). Those subjects who have failed to fast for 8 hours should return for their blood draw following an 8-hour fasting period. At the visit, the following procedures will be performed:

- Randomization
- Recording of vital signs
- Measurement of body weight
- Recording of AEs
- Recording of concomitant medications
- Physical examination
- Electrocardiogram (ECG)
- Chemistry panel
- Hematology
- Urine sample for complete urinalysis
- Serum lipid profile

- ApoA-I and ApoB
- Dispense investigational product
- TLC counselling

#### **4.2.2 Visit 5 (Week 6)**

Subjects will be required to fast for 8 hours (water permitted) prior to Visit 5 (Week 6). Those subjects who have failed to fast for 8 hours should return for their blood draw following an 8-hour fasting period. At the visit, the following procedures will be performed:

- Recording of vital signs
- Recording of AEs
- Recording of concomitant medications
- Chemistry panel
- Serum lipid profile
- Investigational product compliance
- TLC counselling

#### **4.2.3 Visit 6 (Week 13)**

Subjects will be required to fast for 8 hours (water permitted) prior to Visit 6 (Week 13). Those subjects who have failed to fast for 8 hours should return for their blood draw following an 8-hour fasting period. At the visit, the following procedures will be performed:

- Recording of vital signs
- Recording of AEs
- Recording of concomitant medications
- Chemistry panel
- Serum lipid profile
- Dispense investigational product
- Investigational product compliance
- TLC counselling

